2.4.1.2 Multiple assessments within visit windows

When there are *multiple assessments* in a particular visit window, the following rules are applied to select one value “representing” the subject in summary statistics in a visit window (See Table 2-4).

For baseline assessment definition see Section 2.1.1.3. For post-baseline visit windows the following applies (unless otherwise specified):

- for *quantitative variables*, the *closest* to the actual visit is chosen (if two assessments have the same distance, then the earlier one will be chosen);
- for *qualitative variables*, the *worst* record is selected. It is noted that in the analyses performed, *worst* case is always well defined (e.g., for urine protein values “+” and “++”, the *worst* case is defined as “++”),
- in case qualitative variables are based on quantitative variables, e.g. PASI 90 response, the visit will be assigned to the quantitative variable, and this visit will be used for the derived qualitative variable.

Table 2-4 Rules for selecting values for analysis within a given visit window

Timing of measurement	Type of data	Rule
Baseline	All data	See Section 2.1.1.3
Post-baseline efficacy	All data [REDACTED]	The measurement closest to the target day will be used. In the event two measurements are taken equally apart (e.g., 1 day before target date and 1 day after), the earlier one will be used. If two measurement are taken on the same day then select the first one using eCRF visit number.

Timing of measurement	Type of data	Rule
[REDACTED]	[REDACTED]	If two measurement have been taken on the same day and same visit then select the worst. [REDACTED]
Post-baseline safety	Summary visit information (e.g. laboratory values, vital signs, etc.)	The (non-missing) measurement closest to the target day will be used. In the event two measurements are taken equally apart (e.g., 1 day before target date and 1 day after), the earlier one will be used. If two measurements are taken on the same day then take the average of these two results
Post-baseline safety	Notable abnormalities (e.g. vital signs) and CTCAE grades for laboratory values	The most extreme measurement in the window will be used. Note this means a subject can have a notably high and notably low measurement within an analysis period.

2.4.2 Prior, concomitant and post therapies

Medications will be identified using Novartis Drug and Therapy Dictionary (NovDTD) including Anatomical Therapeutic Chemical (ATC) code. Prior and concomitant treatments will be summarized by treatment group for the safety set unless otherwise specified. Concomitant treatments will be displayed for the treatment period.

Prior and concomitant medications will be summarized by treatment group in separate tables. Medications will be presented in alphabetical order, by ATC codes and grouped by *anatomical main group* (the 1st level of the ATC codes) and PT. Tables will also show the overall number and percentage of subjects receiving at least one drug of a particular ATC code and at least one drug in a particular anatomical main group.

Prior medications are defined as drugs taken and stopped prior to the first dose of study treatment. Any medication given at least once between the day of first dose of randomized study treatment, and last dose plus 84 days or last (including follow-up visits) whichever occurs

earlier will be a **concomitant** medication, including those which were started pre-baseline and continued into the treatment period.

Separate psoriasis specific summaries of prior and/or concomitant medication will be presented as in Table 2-5, but as well for topical, phototherapy and photo chemotherapy (yes/no) using the randomized set.

In addition, medical procedures and significant non-drug therapies as coded in MedDRA will be summarized.

Prior or concomitant medication will be identified based on recorded or imputed start and end dates of medication taken. Further rules will be given in Section 5. Summaries will be based on the safety set.

Table 2-5 Subgroups based on the previous psoriasis therapy

Level 1 description	Level 1 outcome	Level 2 description	Level 2 outcome
previous therapy	yes/no		
systemic	no		
	yes	number	1
			2
			>=3
		failure*	no
			yes
biologic	no		
	yes	failure*	no
			yes
		type of previous biologic	
		anti-p40	no
			yes
		anti-TNF	no
			yes
non-biologic systemic	no		
	yes	failure*	no
			yes
		failure* to at least 2	no
			yes

only selected subgroups will be used for reporting

*: at least one therapy with lack of primary efficacy or lack of secondary efficacy or lack of tolerability

2.5 Analysis of the primary objective

The primary analysis of the study is a Bayesian analysis, chosen to allow the direct incorporation into the analysis of information about placebo response rates from historical data. Literature and internal Novartis pediatric and adult plaque psoriasis studies were reviewed to provide the basis for assessing efficacy compared to a historical placebo. All analyses included in this study are based on clinically appropriateness and alignment of definitions (endpoints, clinical disease population, and time point of assessment). Integrated in the analysis are data from four Novartis reported secukinumab adult placebo-controlled trials (CAIN457A2302, CAIN457A2303, CAIN457A2308 and CAIN457A2309) and pediatric study CAIN457A2310. Pediatric placebo-controlled trial data from literature on other biologics at study level data will be utilized ([Paller 2008, Landells et al 2015](#)). A historical placebo control is obtained through the Bayesian meta-analytic-predictive (MAP) framework ([Spiegelhalter et al 2004, Neuenschwander et al. 2010](#)). Further details on the historical data included are provided in Section 3 and Table 3.1. Note, placebo response rates for study CAIN457A2310 will be available prior to the reporting of this study and therefore utilized in this analysis.

2.5.1 Primary endpoint

The co-primary efficacy variables are PASI 75 response at Week 12 and IGA mod 2011 0 or 1 response at Week 12. Analysis of the primary variable will be performed on each treatment group (AIN457 high vs. historical placebo and AIN457 low dose vs. historical placebo) separately on the FAS population.

2.5.1.1 Definition of PASI and related variables

The investigator or trained qualified designee will complete the PASI assessments. Whenever possible, the same evaluator should perform this assessment at all visits.

The total BSA affected by plaque-type psoriasis will be estimated from the percentages of areas affected, including head, trunk, upper limbs and lower limbs (see below for PASI assessment). The following calculations will be done: each reported percentage will be multiplied by its respective body region corresponding factor (head = 0.1, trunk = 0.3, upper limbs = 0.2, lower limbs = 0.4). The resulting 4 percentages will be added up to estimate the total BSA affected by plaque-type psoriasis.

A PASI score ([Fredriksson and Pettersson 1978, Weisman et al 2003, Gottlieb et al 2005](#)) will be derived as indicated in Table 2-5. The head, trunk, upper limbs and lower limbs are assessed separately for erythema, thickening (plaque elevation, induration), and scaling (desquamation). The average degree of severity of each sign in each of the four body regions is assigned a score of 0-4. The area covered by lesions on each body region is estimated as a percentage of the total area of that particular body region. Further practical details help the assessment:

- The neck is assessed as part of the head.
- The axillae and groin are assessed as part of the trunk.
- The buttocks are assessed as part of the lower limbs.
- When scoring the severity of erythema, scales should not be removed.

Because the head and neck, upper limbs, trunk and lower limbs correspond to approximately 10%, 20%, 30% and 40% of the body surface area, respectively, the PASI score will be calculated using the formula:

$$\text{PASI} = 0.1 (E_h + I_h + D_h)A_h + 0.2 (E_u + I_u + D_u)A_u + 0.3 (E_t + I_t + D_t)A_t + 0.4 (E_l + I_l + D_l)A_l,$$

where E, I, D, and A denote erythema, induration, desquamation, and area, respectively, and h, u, t, and l denote head, upper extremities, trunk, and lower extremities, respectively (see Table 2-6).

PASI scores can range from a lower value of 0, corresponding to no signs of psoriasis, up to a theoretic maximum of 72.0.

The investigator is responsible for collecting the components or scoring signs and total regional area for all visits. PASI and total BSA calculations will be performed by investigator at screening and randomization only. The PASI scores will be calculated by Novartis and will be used in the analysis and for derivation of PASI response values (see below). [REDACTED]

[REDACTED]

Table 2-6 The PASI scoring system

Body region	Erythema (E)	Thickening (plaque elevation, induration, I)	Scaling (desquamation, D)	Area score (based on true area %, A)*
Head (H) [†]	0=none	0=none	0=none	0 = no involvement
	1=slight	1=slight	1=slight	1 = >0-<10%
	2=moderate	2=moderate	2=moderate	2 = 10-<30%
	3=severe	3=severe	3=severe	3 = 30-<50%
	4=very severe	4=very severe	4=very severe	4 = 50-<70%
				5 = 70-<90%
Trunk (T) [‡]	0=none	0=none	0=none	6 = 90-100%
	1=slight	1=slight	1=slight	0 = no involvement
	2=moderate	2=moderate	2=moderate	1 = >0-<10%
	3=severe	3=severe	3=severe	2 = 10-<30%
	4=very severe	4=very severe	4=very severe	3 = 30-<50%
				4 = 50-<70%
Upper limbs (U)	0=none	0=none	0=none	5 = 70-<90%
	1=slight	1=slight	1=slight	6 = 90-100%
	2=moderate	2=moderate	2=moderate	0 = no involvement
	3=severe	3=severe	3=severe	1 = >0-<10%
	4=very severe	4=very severe	4=very severe	2 = 10-<30%
				3 = 30-<50%
Lower limbs (L) [§]	0=none	0=none	0=none	4 = 50-<70%
	1=slight	1=slight	1=slight	5 = 70-<90%
	2=moderate	2=moderate	2=moderate	6 = 90-100%
	3=severe	3=severe	3=severe	0 = no involvement
	4=very severe	4=very severe	4=very severe	1 = >0-<10%
				2 = 10-<30%

* Percentage (not score) of body region (not whole body) affected will be entered in the eCRF.

[†] Neck is assessed as part of the Head (H) body region.

[‡] Axillae and groin are assessed as part of the Trunk (T) body region.

[§] Buttocks are assessed as part of the Lower limbs (L) body region.

The following definitions are possible efficacy evaluations that can be used in clinical trials in psoriasis ([CHMP/EWP/2454/02, 2004](#)):

- **PASI 75 response:** subjects achieving $\geq 75\%$ improvement (reduction) in PASI score compared to baseline are defined as PASI 75 responders
- **PASI 90 response:** subjects achieving $\geq 90\%$ improvement (reduction) in PASI score compared to baseline are defined as PASI 90 responders

2.5.1.2 Definition of IGA mod 2011 score and IGA mod 2011 0 or 1 response

The IGA mod 2011 rating scale for overall psoriatic disease (shown in Table 2-7) has been developed based on a previous version of the scale used in secukinumab phase II studies, and has been updated in collaboration with health authorities (in particular the FDA). The explanations/descriptions of the points on the scale have been improved to ensure appropriate differentiation between the points. It is recommended that the same evaluator conducts the assessments throughout the study whenever possible.

The IGA mod 2011 used in this study is static, i.e., it refers exclusively to the subject's disease state at the time of the assessments, and does not attempt a comparison with any of the subject's previous disease states, whether at baseline or at a previous visit.

Table 2-7 The IGA mod 2011 rating scale

Score	Short Description	Detailed Description
0	Clear	No signs of psoriasis. Post-inflammatory hyperpigmentation may be present.
1	Almost clear	Normal to pink coloration of lesions; no thickening; no to minimal focal scaling.
2	Mild	Pink to light red coloration; just detectable to mild thickening; predominantly fine scaling.
3	Moderate	Dull bright red, clearly distinguishable erythema; clearly distinguishable to moderate thickening; moderate scaling.
4	Severe	Bright to deep dark red coloration; severe thickening with hard edges; severe / coarse scaling covering almost all or all lesions.

Note: Involvement of nails is not part of the assessment.

Subjects require an IGA mod 2011 score at randomization of 3 or 4 in order to participate in the study. Based on this scale, subjects will be considered as **IGA mod 2011 0 or 1 responder** if they achieve a score of 0 or 1 and improve by at least 2 points on the IGA mod 2011 scale compared to baseline.

2.5.1.3 Overview of analysis methods of efficacy variables

An overview of statistical analyses and methods applied to psoriasis efficacy variables is given in Table 2-8.

Table 2-8 Overview of analysis methods for efficacy variables

Variable(s)	Summary of time to event	Summary statistics for binary/ categorical data	Bayesian Analysis	Summary statistics for continuous data	Graphs
PASI 75 response at Week 12		X	X		X*
IGA 0/1 response at Week 12		X	X		X*
PASI 90 response at Week 12		X	X		X*
* dot plot; ** time course plot					

2.5.2 Statistical hypothesis, model, and method of analysis

The statistical hypothesis are that AIN457 high dose or AIN457 low dose is not superior to placebo from historical data in the proportion of subjects with PASI 75 response and IGA 0 or 1 response at Week 12. Data from four adult placebo-controlled trials (CAIN457A2302, CAIN457A2303, CAIN457A2308 and CAIN457A2309) and pediatric placebo controlled trials ([Paller et al 2008](#), [Landells et al 2015](#) and CAIN457A2310) will be used to estimate the historical placebo response rate.

The primary hypotheses of comparing AIN457 doses versus historical placebo data will be evaluated using a Bayesian model fitted to study level data. A Bayesian method has been chosen to allow the direct incorporation into the analysis of information about placebo response rates from historical data through a meta-analytic-predictive (MAP) prior. These historical data will include adult (data from repository CPOOL) and pediatric studies.

First, a logistic regression Bayesian mixed-effects model is fitted to the historical placebo data, including terms study and population. This is built to predict efficacy outcomes of a future pediatric trial taking into account between trial heterogeneity of the control response rate. The adult studies are assigned a smaller weight in comparison to the pediatric studies. This is achieved through allocation to two distinct exchangeability strata which share a common population response rate, but differ in their between-trial heterogeneity parameter $\tau_{s(h)}$. Moderate between-trial heterogeneity (with τ prior set as $\text{HalfNormal}(0, 0.5)$) was defined for pediatric trial data and substantial heterogeneity (with τ prior set as $\text{HalfNormal}(0, 1)$) was defined for adult trial data ([Neuenschwander et al 2010](#)), thus allowing pediatric trial data to be given a higher weight compared to adult trial data. From this model, the MAP prior is derived on the logit scale, and represents the predicted placebo log odds of the pediatric trial, which is used in this study as the comparator. For each endpoint the model was fit using MCMC and the resulting posterior distributions forming the MAP prior are approximated with a parametric

distribution for each endpoint. As parametric distribution a mixture of normal distributions is used, since mixtures can arbitrarily exact approximate any target distribution ([West M 1993](#)). The number of mixture components is chosen automatically using lowest Akaike Information Criteria (AIC) as the criterion. This step is performed prior to the first database lock, and results per endpoint from the best fitting mixture model are presented in Table 2-9.

Table 2-9 Information on placebo priors

Endpoint	Mixture component 1	Mixture component 2	Mixture component 3
IGA 0/1			
Weight	0.555	0.445	
Mean	-3.337	-2.741	
SD	1.0048	0.5311	
PASI 75			
Weight	0.361	0.351	0.288
Mean	-2.555	-2.101	-2.723
SD	0.3866	0.2910	0.9029
PASI 90			
Weight	0.774	0.226	
Mean	-3.487	-4.058	
SD	0.5944	1.0976	

A separate model for each endpoint is fitted on the log odds scale to active data from this study with the term treatment.

These data will be used to calculate the Bayesian posterior of the log odds ratio between AIN457 and placebo treatment response rate in this trial. For the log odds of the AIN457 treatment groups a non-informative prior will be used, whilst the placebo treatment group log odds response rate will be represented through the MAP prior as described above..

Both models described above are fitted separately on each efficacy endpoint (PASI 75, PASI 90 and IGA 0/1) using MCMC in Stan version 2.17.1. The MCMC non-convergence Rhat diagnostic ([Gelman and Rubin 1992](#)) will be monitored for all model parameters. Rhat values much greater than 1.0 indicate sampling problems and the overall number of model parameters with a Rhat value greater than 1.1 will be documented if observed. It is expected there will be zero divergent transitions during the sampling phase of the used hamiltonian monte-carlo (HMC) algorithm implemented in Stan ([Upadhyay et al 2015](#)).

The analysis will report the posterior of the mean log odds ratio as point estimate by its median, its 95% credible interval and the probability of a positive treatment effect which corresponds to the level of evidence for a positive treatment effect. Comparisons with placebo will be

performed for the AIN457 low and high dose group separately on each of the efficacy endpoints at week 12.

Results from the posterior distribution will be plotted to provide a graphical representation.

Analysis of the co-primary variables and key secondary endpoint will be based on the Full Analysis Set (FAS).

Notation

Indexes

$i \in \{1,2,3\}$ labels endpoint PASI 75 (1), IGA 0/1 (2) or PASI 90 (3)

$j \in \{1,2\}$ labels AIN457 treatment arm low dose (1), high dose (2)

$h \in \{1, \dots, H\}$ historical studies

$s(h) \in \{1,2\}$ population

pediatric historical studies have $s(h) = 1$

adult historical studies have $s(h) = 2$

Data

- r responders in placebo group
- \tilde{r} responders in active group
- n patients in placebo group
- \tilde{n} patients in active group

Parameters

- π responder rate placebo
- θ responder rate placebo, log-odds
- μ population response rate placebo
- τ between-trial heterogeneity of trial specific intercept for placebo
- $\tilde{\pi}$ responder rate active
- $\tilde{\theta}$ responder rate active, log-odds
- δ treatment effect as log-odds-ratio with respect to placebo control group

Model

Likelihood

$$r_{i,h} | \pi_{i,h}, n_{i,h} \sim \text{Binomial}(\pi_{i,h} = \text{logit}^{-1}(\theta_{i,h}), n_{i,h})$$

$$\tilde{r}_i | \tilde{\pi}_i, \tilde{n}_i \sim \text{Binomial}(\tilde{\pi}_i = \text{logit}^{-1}(\tilde{\theta}_i), \tilde{n}_i)$$

Hierarchical model (MAP)

$$\theta_{i,h} | \mu_i, \tau_{i,s(h)} \sim \text{Normal}(\mu_i, \tau_{i,s(h)}^2)$$

$$\theta_{i,\star} | \mu_i, \tau_{i,1} \sim \text{Normal}(\mu_i, \tau_{i,1}^2)$$

Treatment effect as log-odds ratio

$$\delta_i = \tilde{\theta}_i - \theta_{i,\star}$$

The final analysis will report for each endpoint i and treatment arm j the probability for a positive treatment effect $P(\delta_{i,j} > 0)$ and the median as a point estimate of the mean treatment difference of AIN457 low dose ($j = 1$) versus historical placebo and AIN457 high dose ($j = 2$) versus historical placebo, and the respective associated 95% credible interval of $\delta_{i,j}$.

Priors

- $\mu_i \sim \text{Normal}(0, 2^2)$ - overall intercept on log-odds scale
- $\tilde{\theta}_{i,j} \sim \text{Normal}(0, 2^2)$ - response rate for active on log-odds scale
- $\tau_{i,s(h)} \sim \text{HalfNormal}(0, s_{s(h)}^2)$ - between trial heterogeneity intercept
- $s_1 = 1/2$ - between trial heterogeneity pediatric data
- $s_2 = 1$ - between trial heterogeneity adult data

2.5.3 Handling of missing values/censoring/discontinuations

Pure non-responder imputation (pNRI) will be used as the primary missing data imputation method for both Bayesian analysis at week 12 and descriptive summaries up to week 52. Missing values with respect to response variables based on PASI score and IGA 2011 categories will be imputed with non-response regardless to the reason for missing data (e.g. premature study discontinuation, missed visit, administrative issues). Subjects with missing baseline or those with all post-baseline missing will be imputed with non-response.

Missing data from this study for Bayesian analysis will be imputed in the SAS platform. A dataset with study level data is constructed in SAS and transferred to RBesT where the MAP analysis will be performed and the results transferred back to SAS for reporting activities.

2.5.4 Supportive analyses

No sensitivity analyses will be performed for Bayesian analysis.

Multiple imputation (MI) will be used as a supportive analysis for the descriptive summary of key efficacy endpoints (see Section 5.4.3) up to week 52. It is a simulation based approach where missing values are replaced by multiple Bayesian draws from the conditional distribution of missing data given the observed data and covariates, creating multiple completed data sets. These completed data sets can then be analyzed using standard methods.

In the multiple imputation analysis the response status will be imputed based on the individual treatment arm information.

Of note: subjects with missing baseline or subjects with all post-baseline missing will be included in the multiple imputation analysis.

The following methods will apply to analysis of the long term efficacy data beyond Week 52:

- Responses variables based on PASI score and IGA mod 2011 categories will generally be presented as ‘observed case’; i.e. all available data for each time point will be included in the analyses.
- Multiple imputation will be used as sensitivity method if appropriate. In general, data will be summarised up to the timepoint where 30-40% values are missing in total.

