## 1.2 Purpose

The purpose of this study is to assess the efficacy of secukinumab at Week 12, based on both PASI 75 and IGA mod 2011 0 or 1 response rates in children and adolescents aged 6 to less than 18 years at randomization with moderate to severe chronic plaque psoriasis who are candidates for systemic therapy.

This study will provide efficacy, safety and pharmacokinetic data to support the extension of label of secukinumab to include children and adolescents (6 years to <18 years) with moderate to severe chronic plaque psoriasis.

Moreover, this study will assess the long-term efficacy, safety and tolerability of secukinumab over a period of up to 4 years to support the long-term use of secukinumab in pediatric patients.

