#### **5.5.6 Rescue medication**

Rescue medication for psoriasis is not permitted in this study

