#### **9.4.3 Handling of missing values/censoring/discontinuations**

The following imputation methods will apply to the missing data for analysis up to Week 52.

- Pure non-responder imputation (includes Bayesian Primary endpoint analysis at Week 12): Missing values with respect to response variables based on PASI score and IGA mod 2011 categories were to be imputed with non-response regardless to the reason for missing data (e.g. premature study discontinuation, missed visit, administrative issues). Patients with missing baseline or those with all post-baseline missing were to be imputed with non-response (in the secukinumab treatment groups).
- Descriptive summaries on response variables based on PASI score and IGA mod 2011 categories will be imputed with multiple imputations (MI) method as sensitivity imputation method. Multiple imputation (MI) is a simulation based approach where

missing values are replaced by multiple Bayesian draws from the conditional distribution of missing data given the observed data and covariates, creating multiple completed data sets. These completed data sets can then be analyzed using standard methods. Within this analysis the PASI score (absolute change from baseline) or IGA mod 2011 categories will be imputed and response variables will be derived based on the imputed scores. In the multiple imputation analysis the response status will be imputed based on the individual treatment arm information.

The following imputation methods will apply to the missing data for analysis of the long term data beyond Week 52:

- Response variables based on PASI score and IGA mod 2011 categories will be generally be presented as 'observed case'; i.e. all available data for each time point will be included in the analyses.
- Summaries on multiple imputation will be provided as sensitivity analysis where appropriate.

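### After Week 52, PASI and IGA response is mainly observed case, with conditional multiple imputation and an open-ended 30-40% stop, so response in years 2-4 may be overstated and can jump when the method changes

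*SAP*

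**What the plan says.** Long-term efficacy is a stated aim. Protocol 1.2 says that "this study will assess the long-term efficacy, safety and tolerability of secukinumab over a period of up to 4 years".

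The handling of missing response changes at Week 52:

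- **To Week 52.** SAP 2.5.3 makes pure non-responder imputation the "primary missing data imputation method for both Bayesian analysis at week 12 and descriptive summaries up to week 52", whatever the reason for the missing value. Multiple imputation supports the descriptive summaries.
- **After Week 52.** SAP 2.5.4 presents response generally as observed case, "i.e. all available data for each time point will be included in the analyses". The next bullet says "Multiple imputation will be used as sensitivity method if appropriate" and then, in that same bullet, "In general, data will be summarised up to the timepoint where 30-40% values are missing in total". The wording is the same in the July 2020 and September 2023 SAPs.
- **Protocol 9.4.3** has the same observed-case rule and a similar conditional one for imputation: "Summaries on multiple imputation will be provided as sensitivity analysis where appropriate". It has no stop at any level of missingness, and SAP Section 4 does not list the stop among changes to protocol-specified analyses.

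Three features of trial conduct bear on this. Protocol 5.5.6 states: "Rescue medication for psoriasis is not permitted in this study". Protocol 5.5.7.2 limits psoriasis co-medication to bland emollients and non-medicated measures. Under Protocol 3.1 and 5.6.2, a subject who stops treatment has the end-of-treatment assessments about 4 weeks after the last dose and then the treatment-free follow-up visits, not the rest of the treatment-period schedule.

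**The concern.** A subject who loses response and wants other active psoriasis treatment has to stop study treatment to get it. Once stopped, that subject soon disappears from the observed-case denominator. If this happens more often to non-responders than to responders, the observed-case rate in years 2-4 describes a group that is doing better than the randomised one.

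Two further points add to this. First, the displayed series moves from a conservative method to an unadjusted one between Week 52 and Week 64, so a curve can rise at that point with nothing having changed in the patients. Second, the stop is a range, with nobody named to choose within it, no definition of the total and no stated scope. If it covers only multiple imputation, the sensitivity analysis ends where missingness is greatest. If it covers observed case too, late visits could go unreported.

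At stake is how durable the response appears over four years, which supports long-term use in children.

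**Working it through.** The plan gives no figure to reproduce here: 30-40% is a reporting rule without a derivation, and the documents state no dropout rate after Week 52. What follows is illustrative. The 65% is the plan's Week 12 planning rate for PASI 75 (SAP Section 3), borrowed only as a convenient value. The dropout rates are assumptions.

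**1. Change of method at Week 52.** Let p be the response rate among observed subjects and d the fraction missing. Non-responder imputation shows p(1 - d); observed case shows p. With p = 65% and d = 10% at both visits:
- Week 52: 0.65 x 0.90 = 58.5%
- Week 64: 65.0%

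The displayed rise of 6.5 points is entirely methodological.

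**2. Selection.** Let R be the true rate in all subjects, and let non-responders be missing k times as often as responders. Responders are then missing with probability d_r = d / (R + (1 - R)k), and observed case shows R(1 - d_r)/(1 - d). With R = 65%:

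| Missing | k = 1 | k = 2 | k = 3 |
|---|---|---|---|
| 30% | 65.0% | 72.2% | 76.5% |
| 40% | 65.0% | 76.2% | 82.8% |

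For 30% and k = 2: d_r = 0.30/1.35 = 0.222, and 0.65 x 0.778/0.70 = 72.2%.

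**3. Bounds.** If observed case shows 65%, the all-subject rate lies between p(1 - d), where every missing subject fails, and p(1 - d) + d, where every missing subject responds:
- 30% missing: 45.5% to 75.5%
- 40% missing: 39.0% to 79.0%

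**4. When the stop would act.** 30% and 40% of 80 subjects are 24 and 32. Under a constant annual loss a, missingness d is reached at week 52 x ln(1 - d)/ln(1 - a). To reach it by Week 208 needs a of about 8.5% for the 30% value (1 - 0.7^(1/4)) and 12.0% for the 40% value (1 - 0.6^(1/4)).

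| Assumed annual loss | Last visit, 30% | Last visit, 40% |
|---|---|---|
| 8% | 208 | 208 |
| 10% | 168 | 208 |
| 15% | 104 | 156 |
| 20% | 76 | 116 |

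At 10-20% annual loss, the choice within the range moves the last summarised visit by 40 to 52 weeks.

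**5. How long a leaver is observed.** The end-of-treatment visit is about 4 weeks after the last dose, and follow-up adds 16 weeks, so data end about 20 weeks after the last dose. With a last dose at Week 100, data end near Week 120 (Day 841). That is inside the Week 116 window of SAP Table 2-3 (Days 772-855), so nothing would be available from the Week 128 window on.

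**The case against.** **Section 2.7 is not visible.** The 2023 change history records a clarification of missing-data methods beyond Week 52 in Section 2.7, which is absent from the public text. It may fix the cut-off, its scope or the status of multiple imputation. This stands, and limits the point to the visible wording of 2.5.4.

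**A reader might infer that late results may never be shown.** The documents do not support that as an outcome. The stop sits in the multiple-imputation bullet, while the separate observed-case bullet includes all available data at each time point, as does Protocol 9.4.3. Even on the wider reading, the stop is not reached by Week 208 at about 8% annual loss or less.

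**A reader might infer that the observed group is selected for response by design.** That too goes further than the text. Lack of efficacy is not among the mandatory stopping reasons in Protocol 5.6.2, so non-responders may stay and count as observed failures. Subjects may also leave for unrelated reasons. A leaver's end-of-treatment PASI and IGA can enter observed case through the study-day windows, and SAP 1.1 lets discontinuers' follow-up data into the treatment period if appropriate. These features soften the selection for about 20 weeks per leaver, but not for the years after.

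**A reader might take the gap between p and p(1 - d) as the bias.** It is not: p(1 - d) assumes that every missing subject failed, so it is only the lower bound.

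**Multiple imputation is planned.** It conditions on earlier scores, can partly correct response-related dropout, and if carried through would give a series that does not change method at Week 52. This stands, except that it is conditional after Week 52 and the syntax shown in SAP 5.4.3 runs only to the primary-endpoint week.

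**The cut-off is not tuned to results.** The range was already in the July 2020 SAP and is triggered by missingness, not response. That is fair, but the value within the range is still unset.

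**Conclusion.** The point holds as a weakness in how years 2-4 are presented. The visible plan rests mainly on observed case, makes its only sensitivity method conditional, and attaches a stop whose value and scope are open. With no rescue and no treatment-period visits after stopping, those rates may overstate durability.

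The size cannot be stated from the documents. On the assumptions above, a true 65% with 30% missing would appear as anything from 65% to about 72% as the dropout ratio goes from one to two, and as 76.5% at three. The 6.5-point jump at Week 52 assumes 10% missing and a constant rate among those observed.

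The co-primary and key secondary endpoints are at Week 12, and response up to and including Week 52 uses non-responder imputation, so none of these is affected. Response over time is a descriptive, exploratory summary in Protocol 9.6. The change below is a cheap improvement in reporting and replaces no planned analysis.

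**What to change.** In SAP 2.5.4, aligned with whatever Section 2.7 already says:

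1. Keep observed case, remove the 30-40% stop, and report every scheduled visit to Week 208 with the number observed in each arm.
2. Beside it, show a supplementary response line with all FAS subjects in the denominator. Count subjects who have permanently stopped study treatment as non-responders, and use the planned multiple imputation for missed visits in subjects still on treatment.
3. Label that line as a conservative bound and plot it from baseline, so that one series keeps the same method across Week 52.

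The cost is SAP wording and one more set of tables and figures from data already collected, with no change to trial conduct. The downside is a less favourable long-term figure, which will understate response to the extent that subjects left for reasons unrelated to their psoriasis.
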